6.6.2 Laboratory values at baseline

For missing laboratory data at Cycle 1 Visit 1 (before the very first administration of study medication) data from preceding visits will be used.

6.6.3 PK parameters / biomarkers

Missing data and outliers of PK data are handled according to BI standards (3).

Missing biomarker data may be imputed. The rules will be described in the Unblinded Report Planning Meeting (URPM) minutes and/or in the CTR.

Plasma concentration data and parameters of a subject will be included in the statistical PK analyses if they are not flagged for exclusion due to a protocol violation relevant to the evaluation of PK or due to PK non-evaluability (as revealed during data analysis, based on the criteria specified below). Exclusion of a subject's data will be documented in the CTR.

Relevant protocol violations may be

- Incorrect trial medication taken, i.e. the subject received at least one dose of trial medication the subject was not assigned to
- Incorrect dose of trial medication taken
- Use of restricted medications.

Plasma concentrations and/or parameters of a subject will be considered as non-evaluable, if for example

- the subject experienced emesis that occurred at or before two times median tmax of the respective treatment (Median t_{max} is to be determined excluding the subjects experiencing emesis),
- missing samples/concentration data at important phases of PK disposition curve.

Exclusion of PK parameters

The analysis data set (ADS) ADPP contains column variables APEXC and APEXCO indicating inclusion/exclusion (APEXC) of a PK parameter and an analysis flag comment (APEXCO). All analyses based on the PKS are based on PK parameters with APEXC equal to "Included", regardless of the analysis flag comment APEXCO.

Exclusion of plasma concentrations

The ADS ADPC (PK concentrations per time-point) contains a column variable ACEXCO containing an analysis flag comment. Exclusion of a plasma concentration depends on the analysis flag comment ACEXCO. For example, if ACEXCO is set to 'ALL CALC', the value will be excluded for all types of analyses based on concentrations. If ACEXCO is set to 'DESC STATS' the value will be excluded from descriptive evaluations per planned time point. If ACEXCO contains the addition 'TIME VIOLATION' or 'TIME DEVIATION' the value can be used for further analyses based on actual times. If ACEXCO is set to 'HALF LIFE' the value will be excluded from half-life calculation only; the value is included for all other analyses.

Further details are given in (3), RD-01 "Noncompartmental Pharmacokinetic / Pharmacodynamic Analyses of Clinical Studies" and RD-03 "Description of Analytical Transfer Files and PK/PD Data Files".

6.6.4 Randomisation and stratification (Interactive Response Technology (IRT) versus CRF) (only for phase II)

In general, the data as reported in the eCRF will be used for analyses.

6.6.5 ECG

If replicate ECG recordings are missing, the arithmetic means per time point will be computed with the reduced (1 or 2) number of recordings.

If single cardiac cycles (also denoted as beats or waveforms) are missing, the arithmetic means per single ECG will be computed with the reduced (1 or 2) number of cardiac cycles.

If baseline is missing, a QTcF/QT interval > 500 msec at any time on treatment will be a notable finding. In case of a missing qualitative ECG finding at baseline, a finding observed on-treatment will be categorized as 'new onset'.

Exposure-response analyses

Missing xentuzumab plasma concentration data in the PK4+ (ADPC dataset) file identified with below lower limit of quantification (BLQ) will be replaced by zero if measured at baseline and by ½ lower limit of quantification (LLOQ) if measured at an on-treatment time point.

When the actual sampling time of the blood sample or of the ECG recording is not available, the pair of plasma concentration and time-matched ECG endpoint will be excluded from the analyses at the corresponding planned time point. Furthermore, all plasma concentrations flagged with 'exclusion' by the PKEXC variable of the PK4+ file (ADPC dataset) will be excluded from the exposure-response analyses.

6.6.6 FACT-P questionnaire and BPI-SF questionnaire

Handling of missing data for the FACT-P questionnaire is described in Sections 5.3 and 9.3. Handling of missing data for the BPI-SF questionnaire is described in Section 5.3.

6.7 BASELINE, TIME WINDOWS, AND CALCULATED VISITS

6.7.1 Baseline

The last measurement observed prior to start of trial medication will be assigned to baseline. Note that for some trial procedures (for example body weight, vital signs, laboratory tests) this may be the value measured on the same day trial medication was started. In these cases it will be assumed that the measurements were taken prior to the intake of any study medication. For tumour assessment, baseline evaluations must be based on Magnetic Resonance Imaging (MRI) or Computed Tomography scans performed no more than 28 days prior to start of trial medication.

Study days and visits will be labelled according to the flow chart of the CTP.

Unless otherwise specified, baseline is defined as the latest time-point before the very first administration of any study medication. If this criterion is not fulfilled then no baseline will be derived, except in the following case: if a patient is entered (phase Ib escalation and expansion parts) or randomised (phase II part), but not treated, the last value we have for the patient is considered baseline.

Laboratory values:

Baseline is defined as the latest time-point before the very first administration of any study medication.

If any of these times are missing and the date of laboratory value is equal to the date of first study drug administration, then the laboratory assessment will be considered as according to protocol, i.e. as prior to first study medication.

ECG

Baseline values will be derived from the triplicate at the time-point closest to but prior to the first administration of study medication.

Quality of Life (QOL) questionnaires

BPI-SF questionnaire is assessed at screening and several time-points thereafter. Baseline assessment is the questionnaire assessment from screening, unless it is missing. In this case, the C1V1 assessment is considered baseline.

FACT-P questionnaire is assessed at several time-points starting at C1V1. Baseline assessment is considered as being the assessment from C1V1.

6.7.2 Time windows for every tumour assessment

In order to identify whether consecutive imaging time-points are missing for a given patient, a nominal time point [8, 16, 24, 36 weeks and every 12 weeks thereafter] will be assigned to each and every image. This is achieved by creating windows for every tumour assessment (modified RECIST 1.1 and bone). The windows are defined in Table 6.7.2: 1 below. Day 1 corresponds to date of randomisation for the phase II part (for phase Ib expansion part it corresponds to the date of first drug intake of xentuzumab). Assigning time windows for images is only needed for phase Ib expansion part and phase II part. This will therefore not be done for phase Ib escalation part.

TSAP for BI Trial No.: 1280.8

Proprietary confidential information © 2017 Boehringer Ingelheim International GmbH or one or more of its affiliated companies

Table 6.7.2: 1 Nominal time-points and windows for imaging

Nominal time-point [weeks from start of therapy]	Due date of imaging [days]	Window [days]
8	57	1 to =< 85
16	113	86 to =< 141
24	169	142 to =< 211
36	253	212 to =< 295
48	337	296 to =< 379
60	421	380 to =<463
every 12 week interval	etc (1)	etc (1)

(1) Due date of imaging = (nominal time point * 7) + 1. To calculate the lower bound of the window, use the middle point between the due date of the previous time point and the current due date + 1. To calculate the upper bound of the window, use the middle point between the due date of the next time point and the current due date.

If a patient does not have an image in one of the windows described above, he will be said to have 'missed an assessment' for that time-point. In case a patient has more than one assessment in one window, the assessment with the latest outcome will be used for the analysis unless a PD has been recorded earlier then PD will be used.

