Trial Protocol Version 12 Page 13 of 241

Proprietary confidential information. © 2022 Boehringer Ingelheim International GmbH or one or more of its affiliated companies. All rights reserved.

20. Tumour assessment: CT or MRI imaging of the chest, abdomen and pelvis at screening and prior to start C3D1 onwards (see below) according to modified RECIST criteria (version 1.1). If clinically indicated, imaging of any other known or suspected sites of disease using an appropriate method (CT scan or MRI) should be performed. After study entry, all lesions identified during the screening should be followed up at all specified imaging time points. The same radiographic procedure must be used throughout the study. See section 5.1.2.1

A bone scan should be performed at screening, prior to the start C3D1and onwards according to schedule below.

Tumour assessment and bone scans will be performed at the following time points until progression/start of further anti-cancer therapy (assessments may be performed up to 7 days prior to the scheduled assessment date):

- At screening: all patients will have a CT or MRI and bone scan at screening, unless valid results are available from a scan performed within 28 days prior to start of study treatment, as part of routine clinical practice
- Week 8 (49-56 days after randomisation)
- Week 16 (105-112 days after randomisation)
- Week 24 (161-168 days after randomisation)
- Every 12 weeks thereafter (i.e., during week 35-36 (245-252 days after randomisation), during week 47-48 (329-336 days after randomisation), etc...)

In the event of an interruption/delay to treatment the tumour assessment schedule should not be changed.

- 21. All patients should have a tumour assessment/bone scan at EOT visit regardless of the reason for discontinuation, unless the last evaluation was performed within 4 weeks of EOT.
- 22. Optional physical examination.
- 23. If not recovered at EOT, or new AE, or drug related death.
- 24. Dispensing of enzalutamide at every weekly visit. However for patients in Arm B and those patients in Arm A which discontinue BI 836845 permanently, from cycle 4 onwards, enzalutamide will be dispensed only on Day 1 of each cycle, e.g. C4D1, C5D1 onwards.
- 25. For more details on patient completion, see section 6.1.3.5

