5.1.3 Phase II

The primary endpoint for the phase II part of the study is PFS based on investigator assessment.

PFS is defined as the time from randomisation until radiological tumour progression in bone (based on PCWG2 criteria) or soft tissue (based on modified RECIST 1.1) or death from any cause, whichever occurs earlier.

Tumour assessments will be performed at screening, week 8, week 16, week 24 and then every 12 weeks thereafter (more details in CTP Flow Chart).

For each follow-up (FU) imaging time-point an overall tumour response will be determined for soft tissue according to modified RECIST 1.1 (R09-0262 and Appendix 10.4 of the CTP) and for bone according to the prostate cancer clinical trials working group (PCWG2) criteria (R13-1642). The overall tumour response for each imaging time-point according to modified RECIST 1.1 will be selected from the following categories: Complete Response (CR); Partial Response (PR); Stable Disease (SD); No disease (ND); Progressive Disease (PD); Non-CR/Non-PD; Not Evaluable (NE). The overall tumour response for each imaging time-point (if clinically indicated) for bone lesion will be selected from the following categories: Non-progressive disease (Non-PD); Progressive disease (PD); Not Evaluable (NE).

Some patients enter the trial without any target or non-target lesion according to RECIST 1.1. Until new lesions appear and a progression is reported for this patient, the response assessment for such patients will be set to No Disease (ND) (see also Section 5.4.7).

For details on the imaging process and RECIST evaluation, see Section 5.1.2 and Section 10.4 of the CTP.

Derivation of endpoint PFS

Derivations below are described in days. However, the endpoints below will be presented in months in the outputs produced for the Clinical Trial Report (CTR).

For patients with 'event' as an outcome for PFS: (according to modified RECIST version 1.1 or PCWG2)

• PFS [days] = date of outcome - date of randomisation + 1.

For patients with 'censored' as an outcome for PFS: (according to modified RECIST version 1.1 or PCWG2)

• PFS (censored) [days] = date of outcome - date of randomisation + 1.

The censoring rules for PFS (i.e. outcome and date of outcome) are given in Table 5.1.3: 1. Clinical disease progression will not be considered for determination of a PFS event, unless the outcome of the progression is death.

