Proprietary confidential information © 2017 Boehringer Ingelheim International GmbH or one or more of its affiliated companies

If patients would have their radiological examinations over a number of days, i.e. target lesions assessed on day x, non-target lesions assessed on day y and new lesion (if applicable) on day z, the following rules will be applied:

- If the overall response is PD, the earliest date of multiple assessments will be taken.
- If the overall response is SD, Non-CR/Non-PD, Non PD, PR, CR or NE, the latest of multiple assessment dates will be taken, i.e. in the case of SD, Non-CR/Non-PD, Non PD, PR, CR, the latest of multiple dates will be used to censor the patients.

For PFS according to RECIST and PCWG2, the date of overall response will be determined for RECIST and PCWG2 separately. In case both RECIST and PCWG2 show PD then the date of PD will be the earliest date of these two. When either RECIST or PCWG2 show PD, then the date of outcome will be the date of PD. In case none of RECIST or PCWG2 shows PD then the latest date of RECIST and PCWG2 will be used for censoring.

Imaging assessments for which NE is assigned as the overall response at an imaging time-point are considered to be missed assessments. Please note that NE does not indicate lack of progression.

Table 5.1.3: 1 Derivation rules for PFS

Situation	Outcome (event or censored)	Date of outcome		
No baseline radiological assessment				
Patient with death on or before the second planned radiological assessment	Event	Date of death		
Patient without death or patient with death after second performed radiological assessment	Censored	Date of randomisation (or first treatment administration, in non-randomised trials)		
Without post-baseline radiological assessments				
Vital status is unknown or patient is known to be alive	Censored	Date of randomisation (or first treatment administration, in non-randomised trials)		
Death prior or on the second planned radiological assessment	Event	Date of death		

Table 5.1.3: 1 Derivation rules for PFS (cont.)

Situation	Outcome (event or censored)	Date of outcome
Death beyond the second planned radiological assessment	Censored	Date of randomisation (or first treatment administration, in non-randomised trials)
With baseline and post-batherapy	seline radiological a	ssessments BUT no other anti-cancer
Alive and not progressed, no more than one consecutively missed radiological assessments	Censored	Date of last radiological assessment

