Alive and not progressed, two or more consecutively missed radiological assessments	Censored	Date of last radiological assessment prior to missed radiological assessments
Progressed, zero or one missed radiological assessment prior to progression	Event	Date of radiological assessment of progression
Progressed, but two or more consecutively missed radiological assessments prior to progression	Censored	Date of last radiological assessment prior to missed assessment
Death but no progression, zero or one missed radiological assessment prior to death	Event	Date of death

Table 5.1.3: 1 Derivation rules for PFS (cont.)

Situation	Outcome (event or censored)	Date of outcome		
Death without progression, but two or more consecutively missed radiological assessments prior to death	Censored	Date of last radiological assessment prior to missed assessments		
Initiation of subsequent anti-cancer therapy				
Subsequent anti-cancer therapy started before progression or death	Censored	Date of last radiological assessment before subsequent anti-cancer therapy		
No baseline and post- baseline imaging and subsequent-anti cancer therapy started prior to a death	Censored	Date of randomisation (or first treatment administration, in non-randomised trials)		

Data will be carefully checked in order to detect missing assessments. In case further rules are needed, these will be discussed at a BRPM and added in a revision of the TSAP.

In order to identify that consecutive imaging time-points are missing for a given patient, a nominal time point [8, 16, 24, and then every 12 weeks thereafter] will be assigned to the assessments. This is achieved by creating windows for every assessment. The windows are defined in Table 6.7.2: 1.

Last evaluable imaging

An evaluable radiological image for the censoring of PFS is an image for which an overall response assessment of SD, Non-PD, Non-CR/Non-PD, PR or CR has been assigned. This is used for censoring of patients without progression at end of trial, or censoring prior to missed assessments or censoring prior to subsequent anti-cancer therapy. If the bone and the soft tissue assessment have been done at different dates, the date of the first assessment will be the date of censoring.

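### SAP 6.7.2 lets a not-evaluable scan override an evaluable one in the same imaging window, so, read literally, a later PFS event can be censored

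*SAP*

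**What the plan says.** Five statements bear on this.

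- **Choice within a window (SAP 6.7.2).** With more than one assessment in a window, "the assessment with the latest outcome will be used for the analysis unless a PD has been recorded earlier then PD will be used". An earlier PD is the only exception.
- **Status of NE (SAP 5.1.3).** NE is one of the overall responses that can be assigned, for soft tissue and for bone. "Imaging assessments for which NE is assigned as the overall response at an imaging time-point are considered to be missed assessments".
- **Missed window (SAP 6.7.2).** "If a patient does not have an image in one of the windows described above", the patient has missed that assessment. This sentence speaks of images, not of evaluable outcomes.
- **Censoring (SAP Table 5.1.3:1).** Two rows censor instead of counting an event: "Progressed, but two or more consecutively missed radiological assessments prior to progression" and "Death without progression, but two or more consecutively missed radiological assessments prior to death". The date is that of the last radiological assessment before the missed ones. With at most one missed assessment, the progression or death counts.
- **Last evaluable imaging (SAP 5.1.3, end).** An image qualifies for setting the censoring date if its own response is evaluable and not PD. The paragraph does not say whether such an image makes its window assessed.

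A second scan in a window can come from the protocol itself. The phase II flow chart states: "All patients should have a tumour assessment/bone scan at EOT visit regardless of the reason for discontinuation", unless the last evaluation was within 4 weeks of the end-of-treatment (EOT) visit.

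**The concern.** The selection rule ranks scans by date and protects only PD. A scan showing the patient free of progression can therefore give way to a later scan that shows nothing, and the window is then counted as if nobody had looked. One such window does no harm. Two in a row change the patient's status in the primary analysis from event to censored.

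Investigator-assessed PFS is the primary endpoint of phase II. Central-review PFS (SAP 5.2.2.3) and PFS in the expansion cohort (SAP 5.2.2.2) take over the same rules. Patients who stop for symptoms are the ones to think of: clinical progression alone is not a PFS event, so they contribute only through a later radiological PD or death, which is what the two-missed rule can remove.

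**Working it through.** **1. The windows.** Inputs: SAP Table 6.7.2:1 and its footnote. Due day = 7 × week + 1, which gives 57, 113, 169, 253, 337, 421 and (week 72) 505. Upper bounds are midpoints of neighbouring due days: (57+113)/2 = 85, then 141, 211, 295, 379 and 463. The windows are 1–85, 86–141, 142–211, 212–295, 296–379 and 380–463, as printed. Their widths are 85, 56, 70, 84, 84 and 84 days.

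**2. The rules applied to constructed patients** (assumed data; SD = stable disease).

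| Patient | Literal reading | Evaluable scan kept |
|---|---|---|
| 1. SD days 55, 110, 165, 250; NE day 285; no scan days 296–379; death day 390 | 212–295 and 296–379 missed: censored | one missed window: death event, day 390 |
| 2. As 1, but PD on day 420 instead of death | same two windows missed: censored | PD event, day 420 |
| 3. SD day 50; NE day 80; no scan days 86–141; death day 150 | 1–85 and 86–141 missed: censored | one missed window: death event, day 150 |
| 4. SD day 55; NE day 80; SD day 110; PD day 165 | one missed window: PD event, day 165 | PD event, day 165 |

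Patient 4 shows that one overridden window is not enough; an adjacent missed or NE window is needed.

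**3. The censoring date.** In patients 1 and 2, the last window not counted as missed is week 24, which gives day 165. The last image with an evaluable response is the one on day 250. In patient 3 the same two routes give day 1 (randomisation) or day 50. With the SAP's conversion (days × 12 / 365.25), patient 1 contributes an event at 12.8 months, or a censored time of 8.2 or 5.4 months.

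**4. Room for a second scan.** Scheduled scans fall 49–56, 105–112, 161–168 and 245–252 days after randomisation (protocol flow chart), so on study days 50–57, 106–113, 162–169 and 246–253. An EOT scan is required if the last scan is more than 28 days old, so from 29 days after it.

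| Window | Earliest scheduled scan: EOT scan shares the window on | Latest scheduled scan |
|---|---|---|
| 1–85 | 50 + 29 = 79, so days 79–85 | 57 + 29 = 86: none |
| 86–141 | 106 + 29 = 135, so days 135–141 | 113 + 29 = 142: none |
| 142–211 | 162 + 29 = 191, so days 191–211 | 169 + 29 = 198, so days 198–211 |
| 212–295 | 246 + 29 = 275, so days 275–295 | 253 + 29 = 282, so days 282–295 |

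The overlap is at most a week in the first two windows and two to three weeks in the next two. Protocol 7.6 expects median PFS of about 3 months (91 days) and 4.3 to 4.6 months (131 to 140 days), so many events are expected where the overlap is narrow.

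**5. Size.** Protocol Table 7.6:2 takes the log hazard ratio as normal with variance 4/events, so P(HR ≤ 0.8) = Φ[(ln 0.8 − ln HR) / (2/√events)]. At 60 events this gives 0.789, 0.698 and 0.194 for true HR 0.65, 0.70 and 1.0; the protocol prints 0.79, 0.70 and 0.19. The number of events lost is not in the documents, so a range is assumed:

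| Events lost (assumed) | Events left | True HR 0.65 | True HR 1.0 |
|---|---|---|---|
| 0 | 60 | 0.789 | 0.194 |
| 3 | 57 | 0.783 | 0.200 |
| 6 | 54 | 0.777 | 0.206 |
| 10 | 50 | 0.769 | 0.215 |

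This captures lost information only. It does not measure bias if the losses differ between arms.

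**The case against.** The best defence is that the SAP need not be read this way. The 6.7.2 sentence on missing images would leave patient 1's window assessed, because it holds an evaluable image. One can also argue that a scan counted as missed is no assessment at all, so the tie rule never comes into play. Both readings are open, and a reader who infers that wrongful censoring follows without interpretation goes too far. But the image sentence cannot be the whole definition, since an NE scan is also an image and 5.1.3 calls it missed. What stands is an unresolved conflict, not a safe rule.

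A reader might also infer that censoring must fall back to the week-24 scan, or to randomisation in the early case. The paragraph on last evaluable imaging supports day 250 or day 50 instead. The event is lost on either date.

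Further points limit the frequency. The overlap is narrow early on. Protocol 5.1.2.1 continues scans after discontinuation until progression or new treatment, so an empty adjacent window is a departure from plan. New anti-cancer therapy before progression or death censors anyway. It is tempting to add that EOT scans in unwell patients are the likeliest to be NE, but nothing in the documents says so.

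Soft tissue and bone are assessed separately, and the SAP does not say how NE in one and non-PD in the other combine for counting windows. The examples assume that the window's selected outcome is NE.

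Finally, the text after Table 5.1.3:1 allows further rules to be discussed at a blinded meeting and added to the SAP. That is a route to a rule; none is written on this point.

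**Conclusion.** The point holds as a gap in the primary-endpoint derivation. On the literal reading, an evaluable non-PD scan followed by NE in the same window, together with an adjacent missed or NE window, turns a real progression or death into a censored time. On the competing reading the event is kept. Two programmers following the SAP could classify the same patient differently, and the censoring date is open as well.

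The effect is probably small. Several conditions must coincide, the number of patients cannot be derived, and even an assumed loss of 10 of 60 events moves the design probability at HR 0.65 by only 0.02. Protocol 7.2 also bases inference on the size of the observed difference rather than on formal testing. A reader might infer that the rule favours one arm; the documents give no basis for a direction. This is a minor point, worth making because the remedy is cheap and best settled before outcomes are seen.

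**What to change.** In SAP 6.7.2, replace the tie rule with: the latest evaluable (not NE) outcome in the window is used, unless PD was recorded earlier in it; a window is missed only if it contains no evaluable outcome. Apply the same rule to investigator and central-review PFS. This brings 6.7.2 into line with the NE sentence in 5.1.3 and makes the two routes to the censoring date agree in the examples above. A further clause could say how NE in one modality and non-PD in the other are combined.

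The cost is one phrase in the SAP and about one line of code; no scan or visit changes. If the primary analysis has already been run under the present text, count by arm the patients with this pattern and, if there are any, repeat the PFS analysis under the revised rule as a sensitivity analysis.
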